#### **HOST FACTORS:**

- Glucocorticosteroid treatment (prednisolone equivalent of ≥ 20 mg/day or >1mg/kg prednisolone for children under 20kg)
- Treatment with other systemic immunosuppressant drugs
- History of diabetes
- Major surgery during current ICU episode
- Renal replacement therapy
- Neutrophil abnormality (e.g. inherited neutrophil deficiency)
- Impaired gut wall integrity (Recent abdominal surgery, biliary tree abnormality, recurrent intestinal perforations, ascites, mucositis, severe pancreatitis, parenteral nutrition)
- Impaired cutaneous barriers to bloodstream infection (Presence of central vascular access device, hemodialysis)
- Colonization with Candida species in  $\geq$  2 sites (Respiratory tract secretions, stool/rectal swab, skin, wound sites, urine and drains that have been in place for ≥24 hours)
- Solid organ transplant

#### **CLINICAL FINDINGS**

Presence of clinical findings consistent with an infectious disease process that are otherwise unexplained (e.g. fever, leucocytosis, increasing inotrope requirement, new or worsening organ failure, signs of intra-abdominal sepsis, failure to demonstrate improvement with broad-spectrum antibacterial treatment)

#### Day 1 - Day 28

- Duration and dose of treatment with each systemic antifungal drug prescribed
- Occurrence of side effects (specifically liver/kidney failure) related to antifungal therapy

#### Day 28

Mortality

EQ-5D-5L questionnaire for adults only, measured on preferably at day 28 but can be completed at a later date.

#### **Day 90**

- Mortality
- Discharge data including:
  - Date of critical care discharge
  - Date of hospital discharge
  - Location on hospital discharge

Doc No: TM09-LB01 Protocol Version 8.0 Final\_27.05.2021 Page 24 of

#### 9.2 Study Procedures

#### 9.2.1 Blood Sampling

Blood cultures will be taken in the usual manner, for the participating study site, in the course of routine care. The standard care blood culture must be obtained within 24 hours of starting antifungal treatment. A 'research' blood sample for testing should be taken at the same time as the standard care sample from an eligible patient,, that is 'paired' with one of the standard care blood cultures. For adults, this will be approximately 14mL. For children, the preferred research sample volume is 4mL, however, this may be either increased or decreased as deemed appropriate by the clinical team up to a maximum of 14mL. If it is not possible to obtain the research blood from the same sampling event as the blood culture then research blood should be obtained as soon as possible within 24 hours of the standard care blood culture being taken, using the same sampling technique as the standard care blood culture it is paired with (i.e. venepuncture or accessing the same vascular device), when possible.

Specimens from other normally sterile sites will be obtained as considered appropriate by the attending physician in the course of normal clinical care.

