## 3.2.2 New rapid tests offer an opportunity for timely treatment decisions to avoid unnecessary treatment

Tests recently introduced to market, such as the new PCR-based tests, as well as BDG tests, can be completed within one working day and offer the opportunity to influence prescribing decisions at an early time-point. Prior to commercialisation of these Candida PCR tests, the performance of a variety of in-house assays has been described in small series. Collectively,

Doc No: TM09-LB01 Protocol Version 8.0 Final\_27.05.2021 Page 13 of

in meta-analyses, these have shown promising accuracy and it is assumed that commercial tests of a similar nature will perform similarly [9]. BDG is a biomarker that has demonstrable potential for improving the diagnosis of a number of fungal infections, in various populations. including candidaemia and deep-seated candidiasis [10-13].

The most obvious advantage these new tests bring over current culture-based techniques is their speed. Although blood cultures tend to become positive after 2-3 days at least 5-days must lapse before they can be declared negative. After 5-days of presumptive antifungal treatment, even though the patient may have improved for a variety of reasons, doctors are usually unwilling to stop treatment since it is uncertain whether the patient's response is due to antifungal treatment or other factors. By comparison, a negative result obtained within 24hrs of starting presumptive treatment is much more likely to guide antifungal treatment, before the patient is seen to have improved. Hence tests that bring timely results are better able to influence decision-making and redirect conventional practices. The new tests may also bring improved sensitivity, hence higher negative predictive values, than conventional culture methods.

Diagnostic accuracy data currently available for these tests consists of small studies in heterogeneous patient groups. While their performance has been assessed in meta-analyses, it is impossible to be certain that the findings from assimilating low-to-moderate quality data in this way are correct. The diagnostic test accuracy study we propose here will meet this need and offer a pathway to practice change and better targeted antifungal prescribing.

Doc No: TM09-LB01 Protocol Version 8.0 Final\_27.05.2021 Page 14 of

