#### 7.1.1 Inclusion criteria:

- 1. Adults and children >4 weeks old.
- 2. Admitted to a UK ICU (level 2 or 3).
- 3. Prescribed systemic antifungal therapy, for suspected or confirmed Candida infection, during the preceding 24 hours.

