#### 7.1.2 Exclusion criteria:

- 1. More than 24 hours systemic antifungal therapy in the preceding 7-days.
- 2. Treatment with antifungal therapy for proven or suspected mould infection (e.g. aspergillosis).
- 3. Neutropenia (absolute neutrophil count <0.5x10^9/L) during preceding 28 days.
- 4. Acute leukaemia or within 12 months of bone-marrow transplantation.
- 5. Hospitalised prisoners.
- 6. Previously enrolled in this study.
- 7. Proven or suspected active infection with COVID- 19.

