#### **Baseline**

- · Age and gender
- Inclusion and exclusion criteria.
- Hospital admission date and location of patient prior to admission
- ICU admission date and main diagnosis
- Date research blood sample obtained for index tests and reference standard test
- Candida colonisation status at non-sterile anatomic sites, as determined by local laboratory testing in the course of normal clinical care
- Drug, dose and start date of systemic antifungal therapy
- Indication for starting antifungal therapy (e.g. for suspected or proven Candida infection)
- Patient characteristics triggering suspicion of Candida infection (e.g. fever, leucocytosis, increasing inotrope requirement, new or worsening organ failure, signs of intra-abdominal sepsis, failure to demonstrate improvement with broad-spectrum antibacterial treatment)
- Severity of illness indicators: APACHE II on admission to ICU (ICNARC case mix programme number) and SOFA score (adults) & PELOD-2 score (children- when available) on the day of recruitment.

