#### 11.5.2 Subgroup Analysis

An exploratory sub-analysis of the main diagnostic accuracy analysis will be undertaken to evaluate variation in accuracy measures in the following subgroups: children; patients with end-organ dysfunction, assessed using SOFA & PELOD-2 (when available) score (for adults and children, respectively); whether antifungal treatment had been administered prior to the research blood sample being obtained; patients with infection due to different Candida species; and patients with candidaemia (vs other types of invasive candidiasis, such as peritonitis). This analysis will be expressed using 99% CI.

Doc No: TM09-LB01 Protocol Version 8.0 Final\_27.05.2021 Page 30 of

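### Section 9.2.1 lets the index-test sample fall up to 48 hours after antifungals start, and neither the yes/no subgroup nor the listed dates can separate short from long exposure

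*Protocol*

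**What the plan says.** **Sampling (Protocol 9.2.1).** The anchor is the culture: "The standard care blood culture must be obtained within 24 hours of starting antifungal treatment". By default the index-test blood is drawn with it: the "research' blood sample for testing should be taken at the same time as the standard care sample from an eligible patient". The fallback, for when one sampling event cannot supply both, is that "research blood should be obtained as soon as possible within 24 hours of the standard care blood culture being taken".

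**Eligibility (Protocol 7.1).** Inclusion criterion 3 reads "Prescribed systemic antifungal therapy, for suspected or confirmed Candida infection, during the preceding 24 hours". Exclusion criterion 1 reads "More than 24 hours systemic antifungal therapy in the preceding 7-days".

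**Rationale (Protocol 3.2.2).** Speed is presented as the main advantage of the tests, because "a negative result obtained within 24hrs of starting presumptive treatment is much more likely to guide antifungal treatment".

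**Analysis (Protocol 11.2 and 11.5.2).** The main analysis estimates the accuracy of each test with no restriction or split by sampling time. One exploratory subgroup, reported with 99% confidence intervals, is defined by "whether antifungal treatment had been administered prior to the research blood sample being obtained".

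**Data listed (Protocol 9.1, Baseline).** The sample entry is "Date research blood sample obtained for index tests and reference standard test". For antifungal therapy the list gives drug, dose and start date. Neither entry mentions a clock time.

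**The concern.** The two windows in section 9.2.1 are chained, and nothing limits their sum. A site can follow the section exactly and draw index blood well into the second day of treatment. That sample then counts equally with one drawn before the first dose.

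The study is meant to support a protocol for early discontinuation (sections 4.2 and 4.3.1), and its accuracy estimates feed the avoidable-days outcome (5.2) and the clinical and economic models (11.4). If treatment reduces what the tests detect, late samples would lower measured sensitivity for a reason unrelated to performance early in treatment. The sponsor evidently considered a treatment effect possible, since section 11.5.2 has a subgroup for it. That subgroup, however, places one hour and 47 hours of exposure in the same stratum. With dates only, it cannot be built reliably when first dose and sample fall on the same day, and a 24-h split cannot be built at all.

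**Working it through.** **1. Maximum interval from treatment start to index sample.** Culture at most 24 h after start, plus research blood at most 24 h after culture: 24 + 24 = 48 h. With default same-event sampling the maximum is 24 h.

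**2. Exposure by type of pairing.** If the culture precedes the first dose, the research sample is still within 24 h of that culture, so treatment exposure is at most 24 h. Exposure above 24 h arises only when the culture was itself taken on treatment.

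**3. What dates can resolve.** Suppose the first dose and the sample share a calendar date. The sample may be before or after the dose, and the dates do not say which. Suppose the sample is dated the day after the first dose. The interval can be anything from minutes to just under 48 h, so it may lie on either side of 24 h.

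**4. The protocol's own planning figures (section 11.1).** Inputs: N = 1250, 5% dropout, 4% prevalence, 95% sensitivity, 92% specificity.
- Evaluable: 1250 × 0.95 = 1187.5, given as 1188. Infected: 1187.5 × 0.04 = 47.5, given as 48.
- 44/48 = 91.7%, with Clopper-Pearson 95% interval 80.0% to 97.7%, as stated.
- Probability that the sensitivity estimate exceeds 90%: with exactly 48 infected, P(X ≤ 4) for X ~ Binomial(48, 0.05) = 0.909. With the number infected also random, Binomial(N, 0.04), it is 0.924 at N = 1188 and 0.929 at N = 1250, in line with the stated 93%.
- NPV power: expected test-negatives 1188 × (0.92 × 0.96 + 0.05 × 0.04) = 1052. An exact two-sided 5% test of 99% (level and sidedness are my assumption) passes with at most 4 false negatives, giving power 0.907 against the stated 90%.

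The planning figures reproduce. The like-for-like baseline for step 5, with 48 infected fixed, is 91% and not 93%.

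**5. Illustration.** Let f be the share of infected patients sampled late and d the loss of sensitivity in them. Neither is in the documents; both are assumed. Pooled sensitivity = 0.95 − f × d. NPV = (0.92 × 0.96) / (0.92 × 0.96 + (1 − sensitivity) × 0.04).

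| f | d | Pooled sensitivity | P(≤ 4 false negatives of 48) | True NPV |
|---|---|---|---|---|
| 0 | – | 95% | 91% | 99.77% |
| 10% | 10 points | 94% | 84% | 99.73% |
| 20% | 20 points | 91% | 56% | 99.59% |
| 30% | 20 points | 89% | 38% | 99.50% |

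Under these planning inputs the true NPV stays above 99% until sensitivity falls below about 78%. The NPV point estimate would therefore show little of such an effect, while the sensitivity estimate and the power would show it.

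**6. Precision of a late stratum.** If 12 of the 48 infected patients were sampled late and 11 were detected, the 99% interval would be about 52% to 100%.

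**The case against.** The strongest reply is that 48 h is the corner of two maxima. Same-event sampling is the default, and the later draw applies only when that is impossible and then as soon as possible. This stands. A reader might infer that accuracy is not measured in the first 24 h at all, and the documents do not support that.

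A reader might also infer that a pre-treatment culture can be compared with index blood taken after a day or more of treatment, with the discordance scored as a false negative. Step 2 rules this out: a pre-treatment culture allows at most 24 h of exposure.

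The eligibility rules govern entry and need not govern sampling. Section 9.2.1 speaks of an eligible patient, which could be read as carrying the 24-h limit to the time of sampling, but the fallback sentence does not say so. This is an ambiguity and not a proven contradiction.

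Section 3.2.2 contrasts a rapid result with a culture that takes five days to be declared negative. It does not define a 24-h estimand, and it concerns the time of the result, not of the sample. Because the tests can take up to a working day, a sample at 24 h would usually report later. A 24-h sampling cut-off is therefore only an approximation to the decision point. Nor do the documents say that avoidable days will be counted as if every result arrived within 24 h; no result time is stated.

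Finally, the case report form and the sample handling guideline are not shown and may hold clock times, and finer strata may be in an analysis plan that is not shown. What remains is that the protocol fixes a yes/no split and lists dates only. An analysis plan cannot supply times that were never collected.

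**Conclusion.** The point holds in a limited form. Section 9.2.1 permits an index sample up to 48 h after treatment start with no stated overall limit, the main analysis pools it with all others, and the only prespecified safeguard neither separates short from long exposure nor can be derived from the listed dates for same-day events. The 48 h is arithmetic on the protocol's own windows and needs no assumption.

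The consequence cannot be sized from the documents: they give neither the share of late samples nor the sensitivity in them, so even the direction of any bias is unknown. Under the assumed values in the table, the chance of at most 4 false negatives among 48 falls from 91% to between 84% and 38%, while true NPV remains at 99.5% or higher. The sample-size figures themselves reproduce and are not in question. This is a worthwhile and inexpensive correction; it does not invalidate the design.

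**What to change.** 1. Record date and time of the first antifungal dose, the paired culture and the research sample.
2. Keep all participants in the main analysis. Add a prespecified sensitivity analysis restricted to samples taken no later than 24 h after the first dose, and run those estimates through the test-based protocol and the models as a scenario. Making the restricted set the sole model input would be a debatable trade-off with about 48 infected patients expected, so it is not proposed.
3. Replace the yes/no subgroup in section 11.5.2 with three strata: before the first dose, up to 24 h after it, and more than 24 h after it.
4. Reconcile section 9.2.1 with section 7.1 by stating whether the 24-h limit applies at the time of sampling. If it does, the third stratum simply collects deviations and samples already taken.

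The cost is a few time fields, one further analysis, and wider intervals in the restricted set by an amount that depends on how many samples are late. Precision in the late stratum will be poor (step 6), so it should be read descriptively.

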#### 9.2.2 Sample Processing and Storage

Arrangements for sample processing and storage are described in the sample handling guideline.

#### 9.2.3 EQ-5D-5L Questionnaire

Health related quality of life (HRQoL) will be measured in adult participants using the EQ-5D-5L administered preferably at day 28 but can be completed at a later date. Where the patient has been discharged from hospital, the questionnaires may be administered by telephone.

#### 9.2.4 Participant Follow Up

Data will be censored at 90 days should patients still be in ICU and/or hospital. Patient survival after discharge from hospital will be determined either from hospital information systems (e.g. electronic care record) or by using the NHS Digital if available in that region or by contacting the GP (which will be undertaken centrally by NICTU staff).

#### 9.2.5 Clinical Management of Patients in the Study

There will be no change to standard care treatment. Results of index tests will not be made available to clinical care teams.

Doc No: TM09-LB01 Protocol Version 8.0 Final\_27.05.2021 Page 25 of

#### 10. DATA COLLECTION & MANAGEMENT

#### 10.1 Data Quality

Data integrity and study credibility depend on factors such as ensuring adherence to the protocol and using quality control measures to establish and maintain high standards for data quality.

The Chief Investigator (CI) and CTU will provide training to site staff on trial processes and procedures including the case report form (CRF) and data collection.

Quality control is implemented by the CTU in the form of Standard Operating Procedures (SOPs), which are defined to encompass aspects of the clinical data management process, and to ensure standardisation and adherence to International Conference of Harmonisation Good Clinical Practice (ICH-GCP) guidelines and regulatory requirements.

Data validation will be implemented and discrepancy reports will be generated following data entry to identify discrepancies such as out of range, inconsistencies or protocol deviations based on data validation checks programmed in the clinical trial database.

#### 10.2 Data Collection

All data for an individual patient will be collected by the PI or designee and recorded in source documents/ electronic CRF for the study. Patient identification on the CRF will be through their unique trial identifier, allocated at the time of recruitment.

Data should be entered onto the online electronic study database as per the CRF entry quidelines.

#### 10.3 Data Management

Following the entry of patient data into the study database, the data will be processed as per the CTU Standard Operating Procedures (SOPs). Data queries will be generated for site staff as required to clarify data or request missing information. The designated site staff will be required to respond to these queries within approximately 2 weeks. All queries will be responded to and resolved within the study database. Any amended information will then be entered in the study database.

Doc No: TM09-LB01 Protocol Version 8.0 Final\_27.05.2021 Page 26 of

## 11. STATISTICAL CONSIDERATIONS

## 11.1 Sample Size

The sample size of 1250 gives 90% power to test the negative predictive value (NPV) > 99% and 93% power of point estimates for sensitivity > 90%.

#### Assumptions:

- (i) In a survey of clinicians, the "minimum acceptable threshold for sensitivity" of a test that would be used to stop empirical antifungals, 90% emerged as an important sensitivity cut-off to influence practice.
- (ii) Based on the above survey, clinicians were asked to select a minimum threshold of NPV to allow discontinuation of antifungals and a value of greater than 98% would satisfy the test performance requirements of all respondents. As the disease prevalence is anticipated to be low, we have set a more stringent criterion of 99% NPV for the sample size calculation.
- (iii) 4% true disease prevalence
- (iv) 92% true test specificity, and 95% true test sensitivity.
- (v) 5% dropout

Among the 1250 participants at least 1188 will provide evaluable data (95%), of whom 48 are expected to have true infection (4%). With up to 4 false negative results with the best index test (or combination), the 95% CI around a point sensitivity estimate of 91.7% would be 80%-97.7%. This indicates the approximate size of the confidence interval envisaged and reflects a degree of precision that is likely to be acceptable to clinicians if the point sensitivity estimate is above 90%.

#### 11.2 Statistical Methods

The main analysis will be undertaken to estimate the diagnostic test accuracy of each index test, expressed as sensitivity, specificity, positive/negative predictive values (at specified prevalence) and positive/negative likelihood ratios. They will be calculated with their respective 95% confidence intervals, to express precision of these measures. The PCR-based index tests will produce a categorical result whereas the BDG test will produce a quantitative result. The BDG results will be classified as positive or negative before data analysis begins and the cutoff value used for this will be based on established manufacturer recommendations and expert opinion (currently 80pg/mL).

Analysis of test combinations will also be undertaken as a secondary analysis and will include assessment of these accuracy metrics for all possible permutations of index test results. Taking account of FDA guidance, use of a constructed reference standard will be used for the main analysis because of the difficulties inherent in other approaches when there is no perfect reference test available. The main analysis will, firstly, be undertaken using the international consensus definition of proven fungal disease, as applied for Candida infection, as the reference standard to classify participants. This is acknowledged as an imperfect standard; while its specificity for fungal disease is accepted to be high, its sensitivity is the main source of imperfection. Therefore, it is foreseeable that use of this reference standard alone in the analysis may lead to underestimation of the specificity of the index tests; this may arise if the reference standard fails to detect participants with true disease in instances where the index tests correctly detect this. This concern will be mitigated by also using the forthcoming availability of an internationally-accepted expert consensus standard for probable Candida infection which has been specifically developed for application to ICU patients.

Therefore, as well as being completed using the definition of proven infection, the analysis will also be undertaken using this definition of probable infection; hence, in a secondary analysis,

Doc No: TM09-LB01 Protocol Version 8.0 Final\_27.05.2021 Page 27 of

the reference standard will be proven + probable Candida infection. This helps to overcome the imperfection in sensitivity implicit in using only the definition for proven infection – although this may trade-off some specificity in the reference standard.

Using this approach, we will produce a range for the diagnostic accuracy metrics based on these two reference standards; this reflects uncertainty in the classification of patients resulting from the absence of a perfect reference standard. In the present study, the reference standard comprising proven + probable infection will be particularly useful since certainty in maximising disease detection is a priority when a test may be used to rule-out infection & stop treatment. When future test users consider adopting the index tests, they will be able to consider both the 'optimistic' and pessimistic' accuracy scenarios depending on whether their intended use of the tests is to rule-in or rule-out infection.

